1.1.3 Clinical experience with AZD8330

D1536C00001 is the first clinical study to be conducted in the AZD8330 clinical development program. Based upon emerging safety data, the study has established a maximum tolerated dose (MTD) of 20mg once daily (OD) dosing. The MTD was defined as a result of 5 adverse events, verbatim investigator reported terms: “hallucination” and “mental status changes” at a frequency of 4 out of 9 patients at 40mg and 1 out of 3 patients at 60mg OD dosing. These adverse events did not meet the key DLT criteria (section 3.1.4.2), but met the following:

- Any toxicity that, in the opinion of the investigator, is sufficiently clinically significant to be considered a DLT.

Apart from the DLT criteria all other adverse events observed have been generally well tolerated.

AZD8330 was well distributed in the tissues clinically, as measured by Vss/F in this study. Pre-clinically there was minimal accumulation observed in the CNS (section 1.1.2). Patients received a single dose of AZD8330 on Day 1, followed by a washout period and OD continuous dosing from Day 8 onwards. The elimination half-life was approximately 15h, therefore steady state was achieved by Day 15 and observed accumulation of AZD8330 was minimal. The adverse events that affected mental status occurred, on average, 32 days (range 15 to 47 days) post- the first dose of AZD8330, no relationship was observed between exposure, as measured by C_{max} and AUC, on Day 1 and 15, and the adverse events defined as mental status changes. Maximal AZD8330 plasma concentrations were observed approximately 0.5 to 1h post-dose and were also not temporally related to the adverse events. There is no known mechanistic rationale to explain these adverse events defining the MTD.

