2.3 Exploratory objectives

Exploratory objectives	Outcome variables
To obtain a preliminary assessment of efficacy of AZD8330	Objective Response Rate (ORR; based on RECIST) for patients with measurable disease Best Overall Response (BOR; based on RECIST) for patients with measurable disease Patients with non target disease will be assessed for complete response, stable disease or progression

To collect a blood sample (optional) for DNA extraction and storage to investigate whether variability in the AZD8330 PK, safety, efficacy or pharmacodynamic results could be explained by differences in the patient's genotype

Correlation of host polymorphisms with variation in PK, safety or response parameters observed in patients treated with AZD8330

^a BNP or NT-proBNP are permitted in the protocol, however these shall be collectively referred to as BNP for the remainder of the protocol.

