4.4 Efficacy and pharmacodynamic measurement and variables

4.4.1 Tumour assessment by imaging techniques using RECIST

The RECIST guidelines for measurable, non-measurable, target and non-target lesions, and the objective tumour response criteria (complete response (CR), partial response (PR), Stable disease (SD) or progression of disease (PD)) are presented in [Appendix C](#). The RECIST criteria will be used to programmatically determine ORR. Patients with non-measurable disease only will be assessed according to RECIST criteria for non-target and new lesions in [Appendix C](#).

Baseline tumour assessments should be performed no more than 4 weeks before the start of study treatment, but should be as close as possible to the start of study treatment. Following date of the first dose with AZD8330, efficacy for all patients will be assessed by objective tumour response every 8 weeks thereafter relative to the date of the first dose with AZD8330. Assessments may be performed +/- 7 days relative to the specified visit date. In addition, patients who progress between scheduled visits should have a radiological imaging for confirmation.

Baseline radiological examination, preferably contrast enhanced CT, will be performed on anatomical coverage to adequately define all areas of disease. Post-baseline imaging should follow and evaluate all lesions identified at baseline. MRI should only be used where CT is not feasible or it is medically contra-indicated.

For patients with measurable lesions, all measurable lesions confirmed and assessed by radiological methods (CT or MRI scans) up to a maximum of 5 lesions per organ and 10 lesions in total, representative of all involved organs, should be identified as target lesions, recorded and measured at baseline, and at the time points specified above.

Non-target lesions will also be monitored throughout the study, and an assessment of non-target lesions will be made and recorded as “present”, “present with progression” or “absent”. Details of any new lesions will also be collected.

If an unscheduled radiological and clinical tumour assessment is performed, and the patient has not progressed, the next scheduled tumour assessment should still be performed at the planned time (as detailed in the study plan) relative to date of first dose of AZD8330.

Tumour assessment will be performed in accordance with the protocol schedule until evidence of one of the following:

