- Progression of disease (patients will be followed for subsequent therapy and survival)
- Death without evidence of progression
- Withdrawal of consent
- Withdrawal from treatment

If a patient has any palliative radiotherapy to a lesion that lesion should not be included in assessment of response, but should be assessed for progression.

A patient will be determined to have progressed if they have progression of target lesions, clear progression of existing non-target lesions, or the appearance of one or more new lesions. Death will be regarded as a progression event in those patients who die before disease progression. Unequivocal malignant disease not identified prior to starting study treatment on additional anatomical imaging (e.g., computed tomography (CT), magnetic resonance imaging (MRI) or bone scan confirmed by X-ray), prompted by symptoms is considered disease progression and should be recorded as new lesions. If progression is uncertain, patients may continue on treatment until the next scheduled assessment (ie, 8 weeks later +/- 1 week) or may have an unscheduled assessment earlier than this if considered appropriate by the investigator.

Lesions must be assessed using the same method and technique on each occasion. Lesions will be recorded on the pCRF page in the same order as they were recorded at screening. Details of any new lesions will also be collected. Response will be calculated in comparison to the baseline tumour measurements obtained before starting treatment. Progression will be calculated in comparison to when the tumour burden was at a minimum. Overall visit response will be recorded on the pCRF.

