4.4.2.2 Derivation or calculation of outcome variable

Best overall response will be calculated as the best response recorded from date of randomisation (taking as reference for progressive disease the smallest measurements recorded since the treatment started) for each patient, and will be used for the summaries of objective response. Best overall response will be determined programmatically based on the RECIST criteria.

ORR is defined as the proportion of patients who have a best response of either CR or PR.

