6.3 Description of analysis sets

Population	Definition
Evaluable for safety	This will include all patients who received at least one dose of study medication ^a .
Evaluable for PK analysis	This is a subset of the safety population that includes all patients who provide AZD8330 concentration data and/or any known major metabolites concentration-time data.
Evaluable for Dose Escalation Evaluation (Part A)	This is a subset of the safety population that includes all Part A patients who have had all PK assessments (Day 1) performed, and who have sufficient safety evaluations performed during 35 days dose period from first dose at the discretion of the Safety Review Committee, or have suffered a DLT.

a If a patient discontinues study medication and starts another anti-cancer therapy, all data after 30-day follow-up period for that patient will be excluded from the assessment of safety.

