6.4.3.2 Tumour response

Summaries of best overall response and Objective Response Rate by initial treatment will be produced, for all patients from the safety population who have a baseline RECIST assessment and at least one follow-up RECIST assessment.

Graphical presentations including the following will be produced:

Waterfall plots for each dose level showing the sum of the changes in target lesions for each patient at week 8 compared to baseline, indicating tumour type for each patient.

Scatter plots of change in lesion length vs pre-dose biomarker levels

Scatter plots of change in lesion length vs biomarker BSR

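### Response summaries leave out dosed patients with no follow-up RECIST assessment, a condition that can only raise the reported ORR or leave it unchanged

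*Protocol*

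**What the plan says.** Section 6.4.3.2 (Tumour response) produces the BOR and ORR summaries by initial treatment "for all patients from the safety population who have a baseline RECIST assessment and at least one follow-up RECIST assessment". The safety population is defined in 6.3: "This will include all patients who received at least one dose of study medication".

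The definitions elsewhere carry no follow-up condition. Section 4.4.2.2 states: "ORR is defined as the proportion of patients who have a best response of either CR or PR". Section 2.3 lists the variable as "Objective Response Rate (ORR; based on RECIST) for patients with measurable disease".

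On timing, section 4.4.1 states that "efficacy for all patients will be assessed by objective tumour response every 8 weeks thereafter", counted from first dose, with a window of 7 days either side. Table 1 puts the first follow-up at Day 57 and has no RECIST evaluation at the withdrawal visit. Section 4.4.1 lists "Withdrawal from treatment" among the events that end tumour assessment. Section 4.5.1.2, however, presumes that a patient who withdraws for a reason other than progression goes on having RECIST assessments.

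On deaths, section 4.4.1 states: "Death will be regarded as a progression event in those patients who die before disease progression".

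Section 6.1 says that no SAP will be prepared because the planned analyses are all in the protocol. The rule in 6.4.3.2 is therefore the stated analysis. Section 6.3 defines no response-evaluable set, and the overall response table in Appendix C (4.4) has no not-evaluable category.

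**The concern.** The denominator depends on something that happens after dosing starts: having a follow-up assessment. Patients who fail that condition are not a random subset. They have died, deteriorated without being imaged, or stopped before about Week 8, and none of them can count as a response. Removing them takes only non-responders out of the denominator.

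What is at stake is the first description of anti-tumour activity by dose. Cohorts have 6 to 9 patients, so one or two exclusions move the percentage visibly. A reader of the summary would not see that early deaths had been left out.

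**Working it through.** **Inputs**
- Denominator rule: section 6.4.3.2.
- First scheduled follow-up: Day 57 with a 7-day window (Table 1, note j). Earliest day: 57 − 7 = Day 50, which is 49 days after first dose.
- Confirmation: section 4.4.2.1 requires CR or PR to be confirmed at least 4 weeks after the criteria are met.
- Cohort size 6 to 9 (section 3.1.4.1); about 70 patients in total (section 3.1.1).
- Number without a follow-up assessment, m: not in the protocol, so assumed over a range.
- Number of responders, r: assumed.

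The protocol gives no ORR target, rate or precision, so there is no stated figure to reproduce.

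**Step 1: direction.** With no follow-up assessment there is no measured response and no confirmation. Every excluded patient is therefore a non-responder.
- ORR in all dosed patients with a baseline assessment: r/n
- ORR under 6.4.3.2: r/(n − m)
- Ratio: n/(n − m), which is never below 1

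If r = 0, both are 0%. If m = 0, they are equal.

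**Step 2: size, for assumed r and m**

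| n | r | m | r/n | r/(n − m) | Ratio |
|---|---|---|---|---|---|
| 6 | 1 | 1 | 16.7% | 1/5 = 20.0% | 1.20 |
| 6 | 1 | 2 | 16.7% | 1/4 = 25.0% | 1.50 |
| 6 | 1 | 3 | 16.7% | 1/3 = 33.3% | 2.00 |
| 9 | 1 | 1 | 11.1% | 1/8 = 12.5% | 1.125 |
| 9 | 1 | 2 | 11.1% | 1/7 = 14.3% | 1.29 |
| 9 | 1 | 3 | 11.1% | 1/6 = 16.7% | 1.50 |
| 70 | 7 | 7 | 10.0% | 7/63 = 11.1% | 1.11 |
| 70 | 7 | 14 | 10.0% | 7/56 = 12.5% | 1.25 |
| 70 | 7 | 21 | 10.0% | 7/49 = 14.3% | 1.43 |

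For scale, the exact 95% interval is 0.4% to 64.1% for 1/6 and 0.6% to 80.6% for 1/4. The shift is systematic but small beside the sampling uncertainty of one cohort.

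**Step 3: BOR.** Stable disease also needs a follow-up assessment, so its share rises by the same factor. A patient who dies before any follow-up assessment has progressed under 4.4.1 but appears in no BOR category under 6.4.3.2.

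**Step 4: who is lost.** Early deaths with no prior follow-up assessment are lost on any reading, and so are patients whose deterioration is never imaged. For patients who stop for toxicity, 4.4.1 and 4.5.1.2 give opposite answers. If assessment ends at withdrawal, they are lost unless an unscheduled assessment was done. If it continues, they stay in once assessed.

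**The case against.** The strongest reply is that few patients need be lost. Section 4.4.1 asks for imaging when a patient progresses between visits. Appendix C (4.3.2) asks for efforts to document progression in symptomatic deterioration, even after treatment has ended. Section 3.1.4.3 keeps patients on the assessment schedule after a dose delay or reduction. Section 4.5.1.2 implies continued assessment after withdrawal without progression. The condition is also a RECIST assessment and not necessarily a scan: Appendix C (3.1) allows clinical examination for non-target and new lesions. All of this stands. It narrows the group that is lost but does not empty it.

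A reader might infer from section 1.1.3 that the bias grows with dose. The mental-status events "occurred, on average, 32 days (range 15 to 47 days) post- the first dose of AZD8330", all before the earliest scheduled assessment at 49 days, and 4 of 9 patients at 40 mg had one. The protocol does not support that step. It does not say that these patients discontinued, section 3.1.4.3 allows treatment to resume, and the timing range is not split between 40 mg and 60 mg. Low-dose patients with refractory disease could equally be lost early through rapid progression. A distortion between once-daily and twice-daily dosing is likewise unsupported, and no formal efficacy comparison is planned.

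A reader might also call 6.4.3.2 and the death rule in 4.4.1 a flat contradiction. One says who is summarised and the other says when a patient has progressed, and an early death is a non-response under both. The narrower point stands: the death is missing from BOR.

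Nor does the rule prove that the reported ORR is too high overall. Section 6.4.3.2 does not restrict the set to measurable disease, and including other patients can pull ORR down. That is a separate matter acting in the opposite direction.

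Finally, a response-evaluable set is conventional in a descriptive Phase I summary. ORR and BOR are exploratory (2.3), nothing is tested, and data are listed by dose level (6.4), so exclusions can be traced. Escalation decisions rest on DLTs, safety and PK (3.1.4.1). This limits the weight of the point.

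**Conclusion.** The point holds in a limited form. The follow-up condition in 6.4.3.2 can only raise ORR or leave it unchanged, by n/(n − m), and it drops from BOR early deaths that 4.4.1 regards as progression. With one responder in 6, an assumed loss of 1 or 2 patients moves ORR from 16.7% to 20% or 25%. There is no effect where a cohort has no responders or no early losses.

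The direction follows from the text alone. The size rests on assumed numbers of responders and of patients lost. The number of toxicity withdrawals lost depends on an unresolved conflict between 4.4.1 and 4.5.1.2. The effect could differ between dose groups if early loss differs, but the protocol shows no dose gradient. The summary is exploratory and untested, so this is worth correcting but does not threaten the trial's main conclusions.

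**What to change.** Amend section 6.4.3.2 as follows:
- Base ORR and BOR on all dosed patients with a baseline RECIST assessment. Restrict ORR to measurable disease, as in 2.3. Because 2.3 also ties BOR to measurable disease, show patients with non-target disease only on separate rows.
- Count patients with no follow-up assessment as non-responders in ORR.
- Show them in BOR as PD (death or documented progression) or as not evaluable.
- Keep the present set as a labelled supplementary summary, with the number excluded in each dose group.

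Separately, reconcile 4.4.1 with 4.5.1.2 on whether tumour assessment continues after withdrawal for reasons other than progression.

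The cost is a few lines of text and minor programming. The change of denominator needs no new data. The drawback is a slightly less favourable reported ORR.

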6.4.4 PK/pharmacodynamic relationships

If the data are suitable, the relationship between the plasma AZD8330 and any known major metabolites concentrations/exposure and efficacy/safety parameters will be investigated either using graphical means or appropriate PK/PD software. Details of the pharmacokinetic analyses will be pre-defined prior to data lock.

6.5 Determination of sample size

Part A of the study is not formally powered but is designed to provide adequate tolerability, safety, pharmacokinetic, and pharmacodynamic data.

Part A is also designed to ensure at least 6 evaluable patients are recruited at the dose deemed to be MTD.

The number of patients has been based on both feasibility and obtaining adequate data to assess the biological activity of AZD8330 in tumour in terms of the biomarker pERK in tumour, based on average within-patient reduction in pERK from baseline, as measured using semi-quantitative IHC methods.

Average reductions of 83% on pERK were observed in the first in man study with the MEK inhibitor AZD6244 ([Adjei A et al 2006](#)). The within patient standard deviation of the change from baseline (on the log scale) from this study is estimated as 2.2. 10 patients would therefore provide 80% power to detect an average 70% reduction at the 1-sided 20% significance level.

Therefore approximately 10 evaluable patients at each dose level are considered reasonable to indicate the possibility of biological activity.

The expansion also provides an opportunity to provide a better estimate of the tolerability of each dose for onward development. Expanding the cohort at the maximum tolerated dose from the dose escalation to around 20 provides a stronger estimate of the true DLT rate. For example if the MTD cohort had only 6 patients then:

- If 0 out of 6 DLTs are observed it can be concluded that the true DLT rate is less than 30% with 90% confidence.
- If 1 DLT (16.7%) is observed it can be concluded that the true DLT rate is less than 50% with 90% confidence.

However, with an additional 18 evaluable patients for example:

- If 0 out of 24 DLTs are observed it can be concluded that the true DLT rate is less than 10% with 90% confidence.
- If 4 out of 24 DLTs (16.7%) are observed it can be concluded that the true DLT rate is less than 32% with 90% confidence.

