To determine the pharmacokinetics (PK) of AZD8330 following both single and multiple oral dosing of AZD8330 in patients with advanced malignancies.	Derived pharmacokinetic parameters for AZD8330 will be produced following both a single and multiple oral dosing. This may include C _{max} , t _{max} , AUC, CL/F, and t _{1/2}
To investigate possible relationships between plasma AZD8330 concentrations/exposure and changes in safety and pharmacodynamic parameters.	Output from both graphical and/or appropriate PK/pharmacodynamic modelling techniques
To investigate the effect of AZD8330 treatment on pERK in PBMCs in patients with advanced malignancies.	Change in biomarker pERK in PBMCs

Exploratory

Exploratory Objectives

Outcome Variables

To obtain a preliminary assessment of efficacy of AZD8330.

Objective Response Rate (ORR; based on RECIST) for patients with measurable disease

Best Overall Response (BOR; based on RECIST) for patients with measurable disease

Patients with non target disease will be assessed for complete response, stable disease or progression

To collect a blood sample (optional) for DNA extraction and storage to investigate whether variability in the AZD8330 PK, safety, efficacy or pharmacodynamic results could be explained by differences in the patient's genotype.

Correlation of host polymorphisms with variation in PK, safety or response parameters observed in patients treated with AZD8330

^a BNP or NT-proBNP are permitted in the protocol, however these shall be collectively referred to as BNP for the remainder of the protocol.

Study design

The study is in 1 part, as briefly described below:

Part A: Dose escalation phase

- Part A aims to define the maximum tolerated dose (MTD) of AZD8330, and in the process collect data to allow evaluation of safety, tolerability and pharmacokinetics (PK) during the escalation phase. Six to nine patients will be enrolled per cohort.

The design as described will provide an initial estimate for the maximum tolerated dose (MTD) following once daily (OD) or twice daily (BD) dosing in Part A of the study.

Target patient population

Male and female patients aged 18 years or older who have a cancer that is refractory to standard therapies or for which no standard therapies exist. Inclusion is irrespective of stage of disease.

Investigational product, dosage and mode of administration

AstraZeneca Investigational Products section will supply AZD8330 open labelled clinical study material.

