3.1.1 Study design

This is a Phase I, open-label, multi-centre study to assess the safety, tolerability and pharmacokinetics of an oral formulation of AZD8330 in patients with advanced malignancies who have failed standard therapy, or for which no standard therapies exist. Inclusion is irrespective of stage of disease. The study is expected to recruit up to a maximum of approximately 70 patients from approximately 3 centres within the following countries: United States, and Norway.

The actual numbers recruited is dependent upon the number of dose escalations in Part A.

Reasons for patient withdrawal will be given due consideration when enrolling patients.

The study is in 1 part, as briefly described below:

Part A: Dose escalation phase

- Part A aims to define the maximum tolerated dose (MTD) of the oral formulation, and in the process collect data to evaluate the safety, tolerability and PK profile during the escalation phase. 6 to 9 patients will be enrolled per cohort.

The design as described will provide an initial estimate for the maximum tolerated dose (MTD) following once daily (OD) or twice daily (BD) dosing in Part A.

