4.4.5 Phospho-ERK in matched tumour biopsies (Not applicable)

No longer applicable.

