4.4.6 Other biomarker analysis of tumour biopsy material (Not applicable)

No longer applicable.

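### Section 6.5 justifies patient numbers by 80% power for tumour pERK in about 10 patients per dose level, but the current trial collects no tumour pERK and enrols 6 to 9 per cohort

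*Protocol*

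**What the plan says.** Section 6.5 of the Protocol names two bases for the number of patients. One is feasibility. The other is having enough data "to assess the biological activity of AZD8330 in tumour in terms of the biomarker pERK in tumour", measured by semi-quantitative IHC as a within-patient change from baseline. The variability comes from the first-in-man study of another MEK inhibitor: "The within patient standard deviation of the change from baseline (on the log scale) from this study is estimated as 2.2". From this the section states that "10 patients would therefore provide 80% power to detect an average 70% reduction at the 1-sided 20% significance level". It concludes: "Therefore approximately 10 evaluable patients at each dose level are considered reasonable to indicate the possibility of biological activity". It then discusses an expansion of the cohort at the maximum tolerated dose to around 20 patients, with a worked example of 18 additional patients.

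The rest of Edition 7 describes a different study:

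- **Tumour pERK.** The section that would collect it is now headed "4.4.5 Phospho-ERK in matched tumour biopsies (Not applicable", with the closing bracket. Sections 4.4.6 (other tumour biopsy biomarkers) and 5.4 (tumour biomarker data) are likewise marked as not applicable.
- **Expansion.** Part B is withdrawn in Sections 3.1.5 and 3.4.2.3. The synopsis and Section 3.1.1 say that the study has one part.
- **Cohort size.** Section 3.1.1 says "6 to 9 patients will be enrolled per cohort", the synopsis says the same, and the thresholds for dose-limiting toxicities (DLTs) in Section 3.1.4.1 are written for 6, 7, 8 and 9 patients.
- **Remaining pERK measure.** Section 4.4.4.1 measures TPA-stimulated pERK in PBMCs by flow cytometry, on Day 1 only. Section 6.4.3.1 lists, summarises and plots it by dose group.
- **Testing.** Section 6.4 rules out formal hypothesis testing, and the first sentence of Section 6.5 says that Part A is not powered formally.

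**The concern.** The only power figure in the Protocol refers to an endpoint that is no longer collected, a number per dose level that the cohort rule does not deliver, and a significance level for a test that is not planned. The section also contradicts its own opening sentence.

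The sample-size section is where an ethics committee or a later reader looks for the reason why this many patients are exposed. Here the reason given describes a design that has been withdrawn. The effect on pERK in PBMCs is a secondary objective, and Section 1.2 says that it will inform an assessment of biological activity before further studies start. A reader could therefore carry the 80% over to the PBMC data, where nothing supports it. Section 6.1 says that no separate statistical analysis plan will be prepared, so on the Protocol's own account no later document would correct the text.

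**Working it through.** **Inputs, all from Section 6.5.** Average reduction 70%, so the post/pre ratio is 0.30. Standard deviation of the change on the log scale 2.2. One-sided significance level 20%. n = 10. The base of the logarithm is not stated. Natural log is assumed because it reproduces the stated figure.

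**Method.** One-sample test of the mean within-patient log change.

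- Effect: δ = −ln(0.30) = 1.204
- Standardised effect: 1.204 / 2.2 = 0.547
- Critical value: z(0.80) = 0.842
- Normal approximation: power = Φ(0.547 × √n − 0.842)
- Exact version: noncentral t with n − 1 degrees of freedom and noncentrality 0.547 × √n

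**Reproducing the stated 80%.** At n = 10, 0.547 × √10 = 1.731 and 1.731 − 0.842 = 0.889, so Φ = 81.3%. Noncentral t gives 80.3%. Solving the normal formula for n gives (2.2 × (0.842 + 0.842) / 1.204)² = 9.46, which rounds up to 10. The Protocol's figure is correct for its inputs.

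**Sensitivity to the reading.** At n = 10, log base 10 would give about 46% and log base 2 about 95%. A two-sided 20% level on the natural-log scale would give 64% (t) to 67% (normal). Only natural log with a one-sided level fits the text.

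**Same inputs at the current cohort sizes (illustration only):**

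| n | Noncentral t | Normal |
|---|---|---|
| 6 | 67.3% | 69.1% |
| 7 | 71.3% | 72.8% |
| 8 | 74.7% | 76.0% |
| 9 | 77.7% | 78.8% |
| 10 | 80.3% | 81.3% |

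These rows isolate the effect of cohort size on the Section 6.5 calculation. They are not power figures for the current trial, because 2.2 is a standard deviation for tumour pERK.

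**Each element of the power statement against the current design:**

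| Element | Section 6.5 | Current design |
|---|---|---|
| Tissue and assay | Tumour, semi-quantitative IHC | PBMCs, flow cytometry (4.4.4.1) |
| Standard deviation | 2.2, from another drug's study | None given for PBMC pERK |
| Patients per dose level | About 10 | 6 to 9 (synopsis, 3.1.1, 3.1.4.1) |
| Test | One-sided, 20% level | None (6.4); descriptive (6.4.3.1) |
| Expansion at the MTD | To around 20 | Withdrawn (3.1.5, 3.4.2.3) |

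No row matches. For PBMC pERK the power cannot be computed, since neither a standard deviation nor a test is specified.

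**The case against.** The strongest reply is that this is leftover text with little consequence. No figure is miscalculated. Section 6.5 itself disclaims formal powering, Section 6.4 rules out testing, and PBMC pERK is only summarised and plotted. The conclusion drawn from 10 patients is modest: an indication that activity is possible. The operative cohort size is justified elsewhere, by the DLT thresholds in Section 3.1.4.1 and by Section 3.2.1, which argues for six patients on pharmacokinetic and pharmacodynamic grounds and on escalation properties compared with a 3 + 3 design. No escalation, enrolment or analysis rule uses n = 10.

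Most of this stands, and it limits the point. Several stronger readings are tempting, and the documents do not support them:

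- **That a cohort without a clear pERK effect would count as a negative result at 80% power.** No test is planned, so there is no negative test result. The paragraph names tumour and IHC explicitly, and Section 3.2.2 shows PBMC pERK being analysed across 0.5 to 60 mg in a population model, not only cohort by cohort. This remains a risk of misinterpretation, not an error built into a decision.
- **That the PBMC analysis has 67% to 79% power.** Those figures borrow the tumour standard deviation. The PBMC value could be smaller or larger.
- **That the removed expansion would have supplied the 10 patients per dose level.** Section 6.5 links the expansion to around 20 patients at the maximum tolerated dose and does not say this.

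The reply does not remove the contradiction. The current text still says that the number of patients was based partly on an endpoint that the trial does not measure.

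**Conclusion.** The point holds as an internal inconsistency of moderate severity. The 80% is arithmetically sound for its inputs (80.3% to 81.3% at n = 10, assuming natural logs and a one-sample test) but describes no endpoint, cohort size or test in the current trial. The removed endpoint is the main defect. The cohort-size mismatch alone is small at 9 patients (78% to 79%) and larger at 6 (67% to 69%), and those figures serve only as illustration.

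A reader might infer that the trial is underpowered or needs more patients. That does not follow: it is a descriptive dose-escalation study with a separate rationale for its cohort size. Dose decisions, data collection and the planned summaries do not depend on the faulty paragraph. What is wrong is the stated justification.

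**What to change.** In Section 6.5:

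1. Delete the tumour-pERK basis for the number of patients, the power statement that follows from it, and the conclusion of about 10 evaluable patients per dose level.
2. Delete the leftover text on expanding the cohort at the maximum tolerated dose.
3. Justify 6 to 9 patients per cohort by cross-reference to the DLT rule in Section 3.1.4.1 and to the pharmacokinetic, pharmacodynamic and escalation rationale in Section 3.2.1. Citing the DLT rule alone would drop half of the existing rationale.
4. If a pharmacodynamic statement is wanted, give precision instead of power: the confidence-interval half-width for the mean log post/pre ratio of PBMC pERK, t(n−1) × SD / √n, at n = 6 and n = 9, for a stated time point and confidence level. The standard deviation should come from this trial's own 0.5 to 60 mg data, which Section 3.2.2 says have already been modelled. The synopsis already foresees confidence intervals for pharmacodynamic data where there are enough data.

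The cost is one rewritten section in the next amendment and, if item 4 is kept, a short calculation from data in hand. The Protocol would no longer claim 80% power. No extra patients or assessments are needed.
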